Appendix 1: Perioperative clinical variables recorded.

Pre-operative Factors
Age
Sex
Body mass index (Kg/M ²)
Charleson co-morbidity index
Diabetic
Current smoker
Chronic kidney disease
Medications:
-Steroids
-Immunosuppressants
Preoperative serum albumin
Pathology
-Malignancy
-Inflammatory bowel disease
-Other benign
ASA grade (1-4)
Urgency of operation:
-Elective
-Urgent
-Emergent
Procedure performed
Intra-operative
Skin preparation used:
-Chlorhexidine
-Aqueous povidone-iodine
-Alcoholic povidone-iodine
Duration of Surgery (minutes)
Prophylactic antibiotics given:
-Before induction
-During procedure
Degree of contamination:
1. Clean
2. Clean-contaminated
3. Contaminated
4. Dirty
Operation site:
-Large bowel
-Small bowel
-Both
Ostomy:
-Ileostomy
-Colostomy
Mesh used for a hernia? If so, type?

Blood loss (mL)
Wound length (cm)
Number of staples used to close the wound
Type of Prevena used (peel & place Vs customizable)
Post-operative
Overall post-operative complications (Clavien-Dindo Grade ¹⁴)
Removal of VAC early? If so, for what reason?
VAC leakage
Peri-operative transfusion
Surgical site infection: 1-Superficial 2-Deep 3-Organ space -If so, occurred on which day?
Procedures undertaken for SSI: -Opening of wound -Opening the wound and packing -Exploration of the wound under general anesthesia -Application of a vacuum dressing -Oral antibiotics -Intravenous antibiotics
Wound healing Likert Score (1-10) from wound photographs taken on post-operative day 0, 7 and 30

Appendix 2: Patient post-discharge questionnaire (PDQ)

Please complete the following questionnaire:

Please fill in the date you completed this questionnaire ____/____/____
Have you had any problems with the healing of your wound? YES NO

If you have answered NO you do not need to continue with the rest of the form. Thank you for taking the time to do this. If you have answered YES, please read the following carefully and complete the rest of the form.

Since you were discharged from hospital after your operation, have you noticed any of the following symptoms?

Was there any discharge or leakage of fluid from any part of the wound? Yes No
If yes, was it either;
 Clear or blood stained
 Yellow/green (pus)
 Other-please specify

Please tick any of the following additional symptoms that applied to your wound:

- Pain or soreness in addition to the discomfort experienced following the operation.
- Redness or inflammation spreading from the edges of the wound.
- The area around the wound felt warmer/hotter than the surrounding skin.
- The area around the wound became swollen
- The edges of any part of the wound separated or gaped open.

Did any health care worker take a sample from your wound to send to the laboratory?
 Yes No

If you saw a health care worker because of these symptoms, please indicate who you saw from the list below-

- Primary care physician
- Home care nurse
- Doctor or nurse at the hospital
- Other – please specify
- Did not see one about my wound

Please tell us the date you noticed these symptoms. If you cannot remember the exact date, please give an approximate date
____/____/____

Have you been prescribed antibiotics for an infection in the wound?

Yes No

If yes, who prescribed them? _____

Have you been re-admitted to hospital with an infection of the surgical wound?

To the hospital at which the operation was carried out? Yes No

To another hospital? Yes No

If yes, which one? _____

Other comments _____

To be complete by the trial investigator

Patient reported SSI meets definition Yes No

If yes enter criteria for SSI:

- Criterion 1: Discharge pus + antibiotics prescribed Clinical signs* + dehiscence
- Criterion 2: Clinical signs* + antibiotics prescribed
- Criterion 3: Clinical signs* + antibiotics prescribed

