Secondary endpoints will include length of hospital stay, cost effectiveness, and the clinical efficacy of the device in relation to the degree of contamination, patient comorbidity, and operative demographics. This information will be recorded contemporaneously on standardized clinical

report forms. Data for this study will then be entered into a REDCap database, which uses a MySQL database via a secure web interface with data checks used during data entry to ensure data quality. REDCap includes a complete suite of features to support HIPAA compliance, including a full audit trail, user-based privileges, and integration with the institutional LDAP server. The MySQL database and the web server will both be housed on secure servers operated by the Cleveland Clinic.

Procedures

Preoperative evaluation will include the prospective assessment and recording of demographic data related to the patient and their co-morbidities. Operative details, including any deviation from allocation, will be recorded immediately after the operation (Appendix 1). The post-operative wound will be assessed daily by the attending staff surgeon. A trained reviewer independent from the surgical team performing the intervention will formally assess the wound on post-operative day seven. If the patient is discharged prior to post-operative day 7, an early outpatient assessment will be scheduled for day 7 ± 1 day as is the standard practice of our department. A second formal wound review will be performed at 30 (+/-7) days, which will involve the patient returning to hospital for a physical review of the wound. At this same visit, patients will also complete a supervised, self-reported post-discharge questionnaire (PDQ) with the study investigator to identify any occurrence of SSI during the intervening period between the two clinical assessments. The questionnaire is based on the validated Health Protection Agency surgical site infection surveillance system⁶, which is based on the original CDC definitions (Appendix 2) and has been used in prior high quality randomized trials of SSIs⁶. To our knowledge, this will represent the first time this questionnaire is used in a trial of Prevena™. On day 7 ± 1 day and 30 \pm 7 days a photograph will be taken of the wound to be evaluated by a blinded assessor of wound healing at a later date and scored on a modified 10-point Likert scale (1 = very poorly healed; 10 = fully healed).

Cost Analysis

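### The post-discharge questionnaire lets a patient stop after one question about wound healing, so an infection treated elsewhere and healed between day 7 and day 30 can be scored as no SSI

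*Combined protocol and SAP*

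**What the plan says.** The primary endpoint is superficial SSI within 30 days, diagnosed on CDC criteria (Efficacy outcomes). After discharge, the plan has two formal wound reviews, at day 7 and at day 30 ± 7 (Procedures). For the time between them it relies on a questionnaire: "patients will also complete a supervised, self-reported post-discharge questionnaire (PDQ) with the study investigator", whose stated purpose is "to identify any occurrence of SSI during the intervening period between the two clinical assessments".

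The form in Appendix 2 begins "Have you had any problems with the healing of your wound". After a NO it says: "If you have answered NO you do not need to continue with the rest of the form". The following all come later on the form:

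- discharge: "Was there any discharge or leakage of fluid from any part of the wound", with pus as one of the answers
- pain, redness, warmth, swelling and gaping of the wound
- whether a wound sample was taken
- the date on which symptoms were noticed
- antibiotics: "Have you been prescribed antibiotics for an infection in the wound"
- readmission, here or at another hospital: "Have you been re-admitted to hospital with an infection of the surgical wound"

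The form ends with a block for the investigator, headed "Patient reported SSI meets definition". Its criteria combine pus, clinical signs, dehiscence and prescribed antibiotics.

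**The concern.** The endpoint is whether an infection occurred within 30 days, not whether one is visible on day 30. The questionnaire exists for infections that come and go between the two examinations, yet its opening question concerns healing and leaves the patient to judge what counts as a problem.

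Take a patient whose wound becomes red and drains on day 14, who receives antibiotics from a primary care physician, and whose wound has closed by day 30. That patient may think that the wound healed well and answer NO. The examination then shows a healed wound, and on the form as printed the antibiotic item is not reached.

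The analysis would not expose such a loss. Under the complete-case rule in Statistical analysis, patients with missing outcome data are excluded. A NO is a completed answer, so this patient stays in as event-free. The symptom date also lies behind the stop, so the event would be lost from the Kaplan–Meier and log-rank analyses as well. At stake are under-counting of the primary endpoint, the power that goes with it and, if the loss differs by arm, the treatment comparison itself.

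**Working it through.** **Step 1: the logic of the form.** Each element of the investigator's block is traced to the item that supplies it.

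| Element | Item that supplies it | Reached after a NO? |
|---|---|---|
| Pus | Discharge and its colour | No |
| Clinical signs | Symptom tick-list | No |
| Dehiscence | Wound edges separated or gaping | No |
| Antibiotics | Antibiotic item | No |

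Every criterion needs at least one of these. After a NO, the form as routed cannot yield a patient-reported SSI.

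**Step 2: other routes to detection.**

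- Daily assessment by the attending surgeon and the two formal reviews (Procedures) find infections present at those times. They do not find one that has come and gone between the reviews.
- The investigator supervises the questionnaire (Procedures) and could probe. No text says to ask the skipped items after a NO.
- Cost Analysis collects primary care use by interview at the 30-day visit, and coordinators identify hospital utilization. Either could reveal the episode, but neither is linked to the SSI endpoint.
- Appendix 1 records SSI type, day and treatment, including antibiotics. The treatment fields cover procedures undertaken for SSI, so they presuppose that one has been recognised.

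**Step 3: the plan's own sample size.** Inputs from Statistical analysis: 19.4% v 8.3%, two-sided 0.05, 80% power, 149 per arm. With unpooled variance:

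n = (1.960 + 0.842)² × (0.194×0.806 + 0.083×0.917) / 0.111² = 148.1, rounded up to 149 per arm, or 298 in total.

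The plan's figure reproduces. The pooled formula gives 151 per arm (302).

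**Step 4: power if some SSIs are hidden.** The documents give no miss rate, so the losses below are assumptions. With pooled variance under the null,

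power = Φ{ [d√n − 1.960√(2p̄(1−p̄))] / √(p₁(1−p₁) + p₂(1−p₂)) },

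where d = p₁ − p₂, p̄ is the mean of the two rates and n = 149. With no loss: (0.111×12.207 − 1.960×0.4885) / 0.4822 = 0.824, so power is 79.5%. Multiplying both rates by (1 − loss):

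| Share of SSIs hidden, both arms | Observed rates | Power at 149 per arm | Total N for 80% (pooled) |
|---|---|---|---|
| 0% | 19.4% v 8.3% | 79.5% | 302 |
| 5% | 18.4% v 7.9% | 77.1% | 322 |
| 10% | 17.5% v 7.5% | 74.5% | 342 |
| 20% | 15.5% v 6.6% | 68.7% | 390 |

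The risk ratio stays at 8.3/19.4 = 0.43 in every row.

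**Step 5: what a given loss requires.** Overall loss = f × m, where f is the share of SSIs that arise and resolve between the reviews and m is the share of those patients who answer NO. With f = 0.25, m = 0.2 gives 5% and m = 0.4 gives 10%. A 20% loss needs m = 0.4 with f = 0.5, or m = 0.6 with f = one third. These values too are assumptions.

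**Step 6: unequal loss.** If 10% were hidden in control and 20% in the intervention arm, the rates would be 17.5% v 6.6% and the risk ratio 0.38. The reverse gives 15.5% v 7.5%, a risk ratio of 0.48 and power of 58.7%.

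**The case against.** The strongest reply is that the opening question covers any past problem, not only the present state of the wound. A patient who needed antibiotics for a draining wound would often say YES. An investigator is present, and the printed instruction permits stopping without forbidding the later items. The same visit includes an interview on primary care use, which is the kind of contact in the example above. The endpoint rests on CDC criteria, so a NO on this form is not in itself a verdict of no SSI. Procedures also describes the form as based on a validated system already used in randomized trials.

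Much of this stands, and it limits the point. A reader might infer that these questions are put to nobody who answers NO, or that the questionnaire is the only means of learning of such infections. The documents do not support either: supervision, the cost interview and the utilization data are real chances of detection. What remains is that none of them is required or linked to the endpoint, and that unscripted probing could vary between patients. Whether the stop belongs to the source questionnaire cannot be checked from the documents, so validation neither defends it nor condemns it.

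The assumed losses are also open to challenge. The 19.4% comes from an internal audit whose method of ascertainment is not stated. Treating it as a fully captured rate and then reducing it is itself an assumption.

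**Conclusion.** The point holds as a gap in ascertainment. Followed as printed, the form can turn a treated and healed infection into a non-event for the primary endpoint, and the plan requires no other step that would recover it. The exposure is limited to infections that arise after the day-7 review and resolve before the day-30 review in patients who answer NO.

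Its size is unknown. Equal loss of 5% to 20% would cost about 2 to 11 points of power (79.5% down to 77.1% or 68.7%). The upper end is probably high, given the narrow window.

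A reader might go further and infer that the form biases the comparison, for example by supposing that events are hidden in one arm only. The documents do not show this. Both arms use the same form, and equal loss leaves the risk ratio unchanged. Unequal loss is possible because gauze and the device are visibly different, no patient blinding is described, and the patient judges the opening question. No direction or size can be derived.

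The change is worth making because it is cheap and protects the primary endpoint, not because a large error has been shown.

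**What to change.** 1. Delete the stop instruction in Appendix 2. At the supervised day-30 visit, ask every patient in both arms the discharge, symptom, symptom-date, wound-sample, antibiotic and readmission items, whatever the answer to the opening question.
2. Complete the investigator's SSI block for every patient.
3. State in Procedures that wound-related contacts or readmissions found through the Cost Analysis interview or the utilization data are checked against the CDC criteria for the endpoint.
4. Keep the opening question as a recorded item, so that the result under the present routing can be reported as a sensitivity analysis.

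The cost is a few more minutes at a visit that already takes place, plus the check in item 3. The drawback is a change to the routing of a form described as based on a validated system, although no item is reworded.
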